Appendix V: Qualitative Guide for In-Depth Interviews (IDIs) for Providers

Introduction

2739 *[~5 minutes]*

27402741

2736

27372738

Interviewer will introduce herself to the provider.

27422743

2744

2745

2746

2747

2748

Thank you for coming today to participate in this interview. We have asked you to participate in this discussion because you provide care and treatment services for individuals who are at higher risk for acquiring HIV. We're conducting this interview to get your input on a point-of-care test that we used in the PUMA study. As you know, this test can measure a person's adherence to pre-exposure prophylaxis (PrEP) by measuring whether tenofovir is found in the person's urine. The goal of this interview is to understand your feelings about this test and to discover potential applications and use cases for this test.

274927502751

2752

2753

2754

2755

2756

2757

2758

2761

We really appreciate you taking the time to talk with us today. The interview should take about 30-60 minutes. We are going to audio record the conversation in order to capture all the details and summarize them later on. For that reason, please do not use your name, other people's names, or organization names to ensure we maintain the confidentiality of the interview. We will also be taking notes during the discussion to use as a reference. After we've transcribed the interview, we will delete the audio recording. Please remember that participation in the interview is completely voluntary, and you may decide to not answer any question as you wish, and you can leave at any time.

27592760

Please feel free to think out loud and answer questions as honestly as possible. And remember that there are no right or wrong answers.

27622763

Are there any questions before we begin?

Do I have your permission to record this discussion? [If provider answers yes, turn on audio recorder.]

2766

2767

2770

2771

2773

2775

Discussion Guide

Probes:

2768 1. To begin, please tell me about your role in the PrEP program.

- a. What do you do on a day-to-day basis?
- b. How do you interact with patients on PrEP?
- 2772 2. How long have you been in this role? (years/months)
 - 3. How do you monitor or assess PrEP adherence at Thika clinic? If at all?
- 4. How easy or difficult is PrEP adherence for your PrEP clients?
 - a. Would you say non-adherence is common?

- 5. How comfortable are women in reporting adherence challenges with PrEP to you or other providers in the clinic? Please explain.
- 2778 6. Does the clinic provide counsel or support around PrEP adherence- trying to take PrEP every day? Please tell me about that.
 - a. Please give some examples of the support services are provided. (For example, do providers spend time counselling patients on the importance of taking PrEP every day? If so, how often is this done?)
 - b. What do you think about the quality of support provided to PrEP clients to improve their adherence? Is it helpful? Are clients responsive to this support?

II. Present the urine assay strip picture

2780

2781

2782

2783

2784

27852786

2787

2788

2789

2790

2791

279227932794

2795

2796

2797

2798

2799

2800

2801

2802 2803

2804

2805

2806

28072808

[Interviewer to bring out the rapid strip urine picture below and show it to the provider]

Interviewer: This is a new test that was developed that can be used to measure people's adherence to PrEP during their clinic visit. We used this in the PUMA study and half of the clients received counseling based on the results of this test and half of the clients received standard-of care counseling.

You saw that all the client has to do was to provide a urine sample, and the provider then dips this strip into the urine sample (up to the test line indicated) and the strip will tell the provider the results at that moment (within about 5 minutes).

The strip tells the provider whether the client has taken their PrEP drugs (yes/no) in the last 4 days. A colored line at the top of the test when dipped into urine means no (has NOT taken PrEP drugs in the last 3 days) and no colored line means YES (has taken PrEP drugs in the past 3 days).

- If the test shows no colored line, it means that person has taken PrEP in the past 4 days (YES)
- If the test shows a colored line, this means that the person hasn't been able to take their PrEP pills for a while (NO)
- Please note that this is the opposite of other rapid tests that we are familiar with, such as pregnancy tests.

III. Elicit feedback about the test

- General thoughts on clarity of test: Now I'm going to ask you about what you thought about this new test.
- 2811 1. What were you first thoughts about this test?
 - a. What do you like about it?
 - b. What do you dislike about it?
 - 2. How clear were the results to you? Or was it confusing? What makes these results clear or confusing?

2818

2819

2820

2821

2822

2823

2824

2825

2826

2812

2813

2814

Applications of PrEP Adherence Testing

- 1. Do you think there would be any benefits or negative effects of using this test on your HIV-negative clients? If yes, what are they and why?
- 2. Would you consider using this test on all of your HIV-negative clients or just a subset? If just a subset, which ones and why? [Probe: If you think the test would be best for only a subset, how would you minimize stigmatization of that subset of clients?]
- 3. For the HIV-negative clients whom you would use this test on, how frequently would you test them and why?
- 4. If you received test results for an HIV-negative client that showed less than perfect PrEP adherence, how would you use the results to support your clinical decision making? Would you do anything differently than what you are currently doing for poor adherence? Why?

2827 2828 2829

2830

2831

2832

2833

2834

Feasibility and Acceptability of PrEP Adherence Testing

- 5. Do you believe implementing this type of test would be feasible in your clinic or in another setting? Why or why not?
- 6. Do you think providers need training to deliver these test results? Why/why not?
- 7. How do you think this test could be implemented? That is, who would do the test? Where would the test be done? Who would give the results? When would the results be given?

2835 2836

2837

2838

IV. Conclusion

8. We have reached the end of our interview. Do you have any other concerns or thoughts about this test that we have not yet discussed? Is there anything that we didn't ask that we should have asked?

2839 2840 2841

[Interviewer]: Thank you again for participating in our study!

Appendix VI: SOP for Performing and Interpreting Urine Tenofovir Adherence Assay

SOP for Performing and Interpreting Urine Tenofovir Adherence Assay

2845 2846

2847

2848

2849

2842

2843 2844

- 1. Present client with a cup and ask them to please provide a urine sample. Of note, there is no need to clean the urethra prior to urine collection. The client can just urinate into the cup (about 5-10mL). Please ask them to urinate into the toilet if they have excess urine after filling the cup to the line.
- 2850 2. Please ask the client to screw the lid on to the urine cup after collection and bring it back out to 2851 the provider.
- 2852 3. The provider (using gloves) should use the dropper provided with the urine test to drip 3-4 2853 drops of urine from the urine cup into the divot of the urine test strip (indicated by blue arrow on 2854 below picture).
- 2855 4. After putting the urine drops on the urine strip test, please lay it on a paper towel and let it 2856 develop for 3-5 minutes
- 2857 5. Please take the sheet provided (table 2858 shown below) and write in the participant 2859 ID in the first column.
- - 6. The control line should turn positive no matter what the adherence line shows. Please mark the sheet provided in the second column with a "Y" for yes if the control line turns positive. If the control line does not turn positive, please mark "N" for no and use another test.

2860

2861

2862

[figure not shown]
2863

2864

2868

2869

Urine rapid strip assay picture

Participant ID number	Dark control line present (Y/N)	Test line present (Y/N)

2870 2871

2872

2873

2874

2879

- 7. The test line will appear if the client is NOT taking his/her PrEP and be absent (not appear) if the client is taking his/her PrEP. Please mark the sheet provided in the third column with a "Y" for yes if the test line turns positive. If the control line does not turn positive, please mark "N" for no.
- 2875 8. Please take a picture of the rapid strip test with the participant ID label next to it so that we can 2876 record the results for the future. (Pictures for QC will be eventually emailed to the UCSF Hair 2877 Analytical Laboratory at [contact]).
- 2878 9. Please discard the urine test strip after marking the sheet and taking the picture

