Counseling on TDF/FTC, its side effect profile, how to take the medication, what to do if side effects are experienced, and the importance of not sharing medication to optimize potential efficacy is performed routinely at each PrEP visit as per the 2016 Kenya PrEP guidelines.

751752753

754

755

756

757

758

759

760

761

762

763764

765

766

767

768

769

770

750

Point of care urine monitoring test

The point-of-care urine-based adherence test is shown in Figure 6 and will be performed for participants in the intervention arm only (urine will be collected and stored without testing until the end of the study for participants in the standard of care arm). The laboratory staff at the Thika Clinic will be trained in the interpretation of this test. As detailed at length in Section 3.3, this competitive assay demonstrates a colored line in samples negative for tenofovir and no line in samples positive for tenofovir (Figure 6) so the laboratory staff will be carefully trained on the interpretation of the test prior to the start of the trial by the PI of the study, the site PIs, and the laboratory manager of the Thika Clinic. Neither the research provider nor the participant will need to interpret the test. The laboratory technologist on site will aid the provider in urine sample collection, perform the test, interpret the test, mark on the test if it is positive or negative, and deliver the results to the research provider for participants in the intervention arm only. The results will be delivered to the research providers for the intervention arm participants from the trained laboratory staff in the form of "yes" versus "no" for recent adherence to tenofovir. The research providers will then immediately deliver the appropriate messaging and counseling based on the urine test results for participants in the study. Of note, pictures of each urine tenofovir assay for participants in the intervention arm will be uploaded into the research database for quality assurance monitoring. After the picture of the test is uploaded into the research database, the used urine test will be discarded in an appropriate manner.

771772773

774

775

776

777

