6. STUDY OUTCOMES AND ANALYSES

6.1. Primary Outcomes

The three primary outcomes for this study will be 1) acceptability of POC urine tenofovir testing among women receiving PrEP in Kenya; 2) feasibility to provide feedback on the POC urine tenofovir assay to participants for healthcare providers, and 3) long-term metrics of adherence as assessed via hair concentrations of TFV and FTC assessed at the 12-month study visit after enrollment.

964965966

967968

969

970

971

972973

974

975

976

977

978

979

980

981

982

983

984

985

986

6.2. Data Collection for Primary Outcomes:

Acceptability for participants taking PrEP: We will conduct a mixed-methods assessment of the intervention arm participants' (all women on PrEP) experiences with real-time monitoring and feedback at the end of the study. A quantitative survey and a qualitative interview guide for indepth interviews of participants will draw from the Information-Motivation-Behavioral skills (IMB) model. 180-187 Quantitative data collection will occur via standardized interviewer-administered questionnaires. Items to be assessed include the following: 1) Feelings about receiving their PrEP adherence results in real time; 2) Likelihood of participating in other studies using a similar design; 3) Likelihood of wanting to receive results of urine testing outside of a study while they are on PrEP; 4) Concern about the privacy and security of the data regarding their urine results; 5) Grading of the potential impact of knowing their urine TFV results on subsequent medication adherence; 6) Advantages and disadvantages of being told about their adherence in real time; 7) Likelihood of taking PrEP just before later study visits because they knew the urine test was being conducted; 8) Preferences regarding a yes/no assay versus an assay that provides information on "high", "moderate" or "low" adherence. A 5-point Likert item format will be used to assess graded items (such as the likelihood of wanting continued urine testing in the context of PrEP; feelings about the urine testing, ranging from negative to positive; concerns about privacy, ranging from low to high; the potential impact of real-time feedback on subsequent adherence, ranging from low to high). Other items (advantages and disadvantages of being told about adherence results) will provide pre-specified options with one "other" option for open-ended text fields.

987 988

989

990

991

992

993

994

995

996

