Small hair samples (~50-100 strands) will be collected at study visits using previously described methods.²³ TFV concentrations in hair samples will serve as the metric for cumulative, long-term adherence to PrEP. TFV and FTC are measured in hair samples at the Hair Analytical Laboratory at the University of California San Francisco (UCSF) using validated methods. The Hair Analytical Laboratory (HAL), and its predecessor (the UCSF Drug Studies Unit), have vast expertise (since 1977) in LC-MS/MS-based methods to analyze drugs in a variety of matrices, including

antiretrovirals (ARVs) in hair. 9,10,30 The trial will assess whether TFV levels in hair increase over time with delivery of the feedback results and the opportunity to perform enhanced adherence counseling. Moreover, the combination of short-term adherence metrics (urine tenofovir assay) and long-term adherence metrics (hair TFV assay) in this study will enable us to determine if there are white-coat patterns of adherence. 35,39,41 For example, positive urine TFV assays but low concentrations of TFV in hair (in intervention arm participants or in both arms, as assessed at the end of the study) are suggestive of white-coat adherence patterns. PrEP refills will be measured through data from the clinic's electronic pharmacy system.

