- 9. Place a participant label on the outside of the folded piece of foil or a label with the patient's ID number, date of collection and study name.
- 2914 10. Place the folded piece of foil inside the Ziplock bag and seal the bag.
- 2915 11. Place another participant ID label on the outside of the Ziploc bag.
- 2916 12. Pictures of the hair collection process for different styles of hair are shown below.
- 13. Hair samples should be stored at room temperature and in a dark place at each processing lab prior to shipment to the testing lab.

Materials required: Scissors, piece of tin foil, patient labels (2), Ziplock bag, and alcohol swabs.

Suggest making these "hair kits" ahead of time.

Step 1: Clean the blades of a pair of scissors with an alcohol pad and allow blades to completely dry.

Clean off blades of scissors between patients.

Step 2: Lift up the top layer of hair from the occipital region of the scalp. Isolate a small thatch of hair (~50-100 fibers of hair) from underneath this top layer.

Can use hair clip to keep top layer of hair away if easier. Can also cut from more than one place if the participant would like that, although 50-100 strands of hair is not cosmetically noticeable.

Step 3: Cut the small hair sample as close to the scalp as possible

[figure not shown]
STRAIGHT HAIR

CURLY HAIR

Protocol Version 6.0

SHORT HAIR
Can let hair fall directly into piece of tin foil when very short/cropped (no need to

BRAIDED HAIRCut hair thatch from in-between braids or dread locks

 Step 4: Keep your fingers on the part of the hair that was FURTHEST away from the scalp and put the hair sample down on an unfolded piece of tin foil.

Step 5: Put a thin label over the end of the hair sample that was FURTHEST away from the scalp.

If hair very short just let it fall into the piece of tin foil and no need to label the distal end. Make sure the

label is thin so you don't cover the hair sample and put

it at the very end.

Step 6: Refold the foil over to completely enclose the hair and place a participant D label on the folded piece of foil

Step 7: Place the folded piece of foil inside the plastic (e.g. Ziplock) bag and seal the bag. Put another patient ID label on the outside of the bag

3035 Appendix VIII: FDA DESIGNATION OF THE URINE TENOFOVIR ASSAY AS NSR

From: [name] < [contact]> Sent: Thursday, October 3, 2019 6:36 PM

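### Participant-ID-labelled strip photographs go to the laboratory that assays hair for the primary adherence outcome, and nothing holds them back until the hair data are locked

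*Combined protocol and SAP*

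**What the plan says.** **Photographs.** Appendix VI, step 8, instructs staff: "Please take a picture of the rapid strip test with the participant ID label next to it". It gives the destination as follows: "Pictures for QC will be eventually emailed to the UCSF Hair" Analytical Laboratory. No date is attached beyond the word 'eventually', and the appendix names no arm. Section 5.5 does name one: "pictures of each urine tenofovir assay for participants in the intervention arm will be uploaded into the research database for quality assurance monitoring". Section 5.10 places the photograph step under the intervention-arm procedures.

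**Hair.** Section 6.1 lists as the third primary outcome "long-term metrics of adherence as assessed via hair concentrations of TFV and FTC assessed at the 12-month study visit after enrollment". Section 6.2, under the heading on hair concentrations, says where the measurement is done: "TFV and FTC are measured in hair samples at the Hair Analytical Laboratory at the University of California San Francisco (UCSF) using validated methods". Appendix VII, step 9, has the foil packet carry a participant label or "a label with the patient's ID number, date of collection and study name"; step 11 adds a second ID label to the outer bag. Section 5.2 schedules hair testing for the end of the study.

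**Masking.** Section 5.7 describes the trial as open-label. No section masks the hair assay, recodes hair samples before shipment, or delays the photographs until the hair results are final.

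**The concern.** Participants and providers cannot be masked in this design, but the hair assay can be, at almost no cost. Routing ID-labelled photographs from one arm to the laboratory that holds the hair samples opens a path to knowledge of allocation that the trial does not need. Photographs are already stored in the research database for quality assurance, and checking how a strip was read does not require the ID under which the hair is filed.

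Hair tenofovir is the only objective primary outcome compared between arms, and the result is meant to inform a larger trial. The laboratory group also co-developed the strip under test (sections 1.2 and 3.3). That implies no misconduct, but it makes documented masking more useful, because an outside reader may ask whether decisions about individual samples were made with allocation known.

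**Working it through.** The plan gives no figure on this point to reproduce. The check sets the sections side by side and counts what is exposed.

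**Step 1: the link.** Photographs carry the participant ID (Appendix VI, step 8). Hair packets carry the participant ID (Appendix VII, steps 9 and 11). Both go to the same laboratory (Appendix VI, step 8; section 6.2). A photograph can therefore be matched to a hair sample.

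**Step 2: what the match reveals.** Section 5.5 says the point-of-care test "will be performed for participants in the intervention arm only (urine will be collected and stored without testing until the end of the" study for the standard-of-care arm). With photographs from the intervention arm only:
- a photograph for an ID indicates the intervention arm, and the visible test line shows that woman's urine result;
- no photograph for an ID indicates standard of care, and no urine result is seen.

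**Step 3: timing.** Hair is assayed at study end. The photographs are sent at an unspecified time. Three orders are possible: before, during or after the hair assays. Only the first two unmask. The text does not choose between them.

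**Step 4: counts, as upper bounds at full attendance.** Inputs are 100–120 women, 50–60 per arm (sections 5.2 and 5.7) and five visits (months 0, 3, 6, 9 and 12).
- Hair samples: 100 × 5 = 500 to 120 × 5 = 600.
- Intervention-arm photographs: 50 × 5 = 250 to 60 × 5 = 300.
- Hair samples at month 12, where section 6.4 places the hypothesis test: 100 × 1 = 100 to 120 × 1 = 120.

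Section 5.12 allows missed visits, so actual counts would be lower.

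**Step 5: where bias could enter.** The shift in the between-arm difference in mean log hair level would be p₁s₁ − p₀s₀. Here p is the fraction of an arm's samples whose handling was altered by knowing the arm, s is the mean log shift in those samples, and 1 and 0 denote the intervention and standard-of-care arms. The documents give none of these four quantities, so no size can be calculated. They do narrow where p can be non-zero. Clearly quantifiable samples are read by LC-MS/MS. Undetectable values are censored at the detection limit, which is also added to every value before logging (section 6.4). That leaves steps for which no written rule was found, chiefly whether to reject or repeat a sample.

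**The case against.** The strongest reply is that this is a possible route to unmasking, not a demonstrated one.

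- **Timing.** If the photographs are sent after the hair assays, nothing is unmasked. This stands, and the point is conditional on it.
- **Which arm.** Appendix VI names no arm, and section 5.2 has stored standard-of-care urine batch-tested locally by laboratory personnel outside the daily running of the study. If step 8 were followed then, photographs could exist for both arms and having one would not by itself mark the arm. This also stands as a possibility. Against it, the opening steps of the appendix describe collecting a fresh sample from a client, and no section describes photographs of standard-of-care strips.
- **Who looks.** Section 14 restricts electronic data to key members of the data team, and receipt by a laboratory is not the same as knowledge by the analyst running the assay. That is fair, but the email in step 8 goes outside the database, and no section separates the person who checks photographs from the person who assays hair.
- **Instrument measure.** The hair assays are validated and, per section 5.1, approved by the Division of AIDS pharmacology quality-assurance programme. Section 6.3 adds that statistical significance on hair is not this pilot's objective. These facts limit the likely harm; they do not close the route.

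A reader might go further and infer that the laboratory learns every woman's arm and urine result. The documents do not support that: on the described procedures no standard-of-care strip result is sent, and knowledge of arm depends on timing. Nor is hair the only objective comparison between arms. Section 6.4 also analyses missed refills, which section 6.2 takes from the pharmacy system, and section 10 plans to compare urine detection.

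**Conclusion.** The point holds as an avoidable and inexpensive weakness, not as evidence that the hair result is biased. It rests on two assumptions that the documents neither confirm nor rule out: that photographs reach the laboratory before its hair assays are complete, and that they come only from the intervention arm, as sections 5.5 and 5.10 describe. Under both, arm could be inferred for all 100–120 women, with strip results visible for the 50–60 in the intervention arm. The month-12 test would involve at most 100–120 samples, and only those needing a discretionary decision would be exposed. The bias cannot be sized from the documents and is probably modest. The change is worth making because it corrects a routing step that the plan itself specifies, for a primary outcome.

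**What to change.** Amend Appendix VI, step 8, in one of two ways: label the QC photographs with a code that cannot be linked to the ID on the hair packets, or release them to the hair laboratory only after the hair dataset is locked. In section 6.2, state that hair is assayed, and that decisions to repeat or reject a sample are made, without knowledge of arm or strip results.

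The first option costs a second set of code labels. The second delays that laboratory's feedback on strip reading; photographs remain available in the research database for quality checks in the meantime. Neither needs extra samples, assays or visits.
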